6. TRIAL OBJECTIVES AND PURPOSE

6.1. Primary Objective

The primary objective is to:

- Determine efficacy by demonstrating achievement of developmental milestone of sitting without support up for at least 10 seconds up to 18 months of age as assessed by WHO Motor Developmental Milestones ([Appendix 5](#)).

6.2. Secondary Objective

The secondary objective is to:

- Determine efficacy based on survival at 14 months of age. Survival is defined by the avoidance of combined endpoint of either (a) death or (b) permanent ventilation which is defined by tracheostomy or by the requirement of ≥ 16 hours of respiratory assistance per day (via non-invasive ventilatory support) for ≥ 14 consecutive days in the absence of an acute reversible illness, excluding perioperative ventilation. Permanent ventilation, so defined, is considered a surrogate for death.

6.3. Exploratory Objectives

Term	Percentage
GMOs	95
Organic	85
Natural	80
Artificial	65
Organic	92
Natural	88
Artificial	75
Organic	98
Natural	92
Artificial	70
Organic	90
Natural	85
Artificial	68
Organic	93
Natural	87
Artificial	72
Organic	96
Natural	91
Artificial	78
Organic	94
Natural	89
Artificial	73
Organic	97
Natural	93
Artificial	76
Organic	91
Natural	86
Artificial	69

Novartis Gene Therapies, Inc.
Investigational Product: AVXS-101

AVXS-101-CL-306
Protocol Version 6.0/Amendment 5/11 Nov 2020

6.4. Safety Objectives

The safety objective is to:

- Evaluate the safety of AVXS-101 in patients with SMA Type 1.

[figure not shown]
7. INVESTIGATIONAL PLAN

7.1. Overall Trial Design

This is a Phase 3, open-label, single-arm, single-dose trial of AVXS-101 (gene replacement therapy) in patients with SMA Type 1 with one or 2 copies of *SMN2*. At least 6 patients < 6 months (< 180 days) of age at the time of gene replacement therapy (Day 1) will be enrolled.

The trial includes 3 trial periods: screening, gene replacement therapy, and follow-up (Figure 4). During the screening period (Days -30 to -2), patients whose parent(s)/legal guardian(s) provide informed consent will undergo screening procedures to determine eligibility for trial enrollment. Patients who meet the entry criteria will enter the in-patient gene replacement therapy period (Day -1 to Day 3). On Day -1, patients will be admitted to the hospital for pre-treatment baseline procedures. On Day 1, patients will receive a one-time intravenous (IV) infusion of the equivalent of AVXS-101 cohort 2 dose received in the AVXS-101-CL-101 trial over approximately 60 minutes and will undergo in-patient safety monitoring over the next 48 hours. Patients may be discharged 48 hours after gene replacement therapy, based on Investigator judgment. During the outpatient follow-up period (Days 4 to End of Trial at 18 months of age), patients will return at regularly scheduled intervals for efficacy and safety assessments until the patient reaches 18 months of age. Any missed visit should be rescheduled as soon as possible, but within the visit windows shown in the Schedule of Assessments (SoA). All visits will be scheduled based on a 30-day month calendar.

After dosing follow-up visits will be conducted according to the SoA ([Appendix 1](#)). All post-treatment visits will be relative to the date on which gene replacement therapy is administered until the patient is 14 months of age, after which all visits will be relative to the patient's date of birth. For the 14 and 18 months of age visits, the patient will return within 0 to 14 days after the date on which the patient reaches 14 and 18 months of age, respectively. The 18 months of age visit will also serve as the End of Trial visit. After the End of Trial visit, patients will be invited to participate in a long-term follow-up study under a separate protocol. Patients who discontinue prematurely will also be invited to participate in the long-term follow-up study.

Figure 4 - Trial Design

Note: After the End of Trial visit at 18 months of age or at the time of early discontinuation patients will be invited to participate in a long-term follow-up study conducted under a separate protocol.

a All post-treatment visits will be relative to the date on which gene replacement therapy is administered until the patient is 14 months of age, after which all visits will be relative to the patient's date of birth. *Note: Depending on the patient's age at dosing, the duration of participation at the end-of-trial visit can vary from approximately 12 months (baby dosed at approximately 6 months of age) to approximately 18 months (baby dosed near birth "0 months of age").* All visits will be scheduled based on a 30-day month calendar.

In an attempt to dampen the host immune response to the AAV-derived therapy, all patients will receive prophylactic prednisolone according to the regimen described in [Section 9.2.1](#).

Efficacy will be assessed by achievement of the key developmental milestone of sitting without support for at least 10 seconds at any time up to and including the 18 months of age trial visit, and survival at 14 months of age (as defined in [Section 14.1.1](#)). Safety will be assessed through monitoring AEs, concomitant medication usage, physical examinations, vital sign assessments, cardiac assessments, and laboratory evaluations ([Section 12](#)).

In the event that unforeseen catastrophic or other serious situations (such as the COVID-19 pandemic) impact the ability to conduct the study on-site, alternative methods of continuing study assessments may be implemented. Alternative visits include phone calls, virtual contacts through teleconsult or videoconference, or visits by site staff/home nursing providers to the patient's home depending on local regulations, institutional policies, and capabilities of the investigative site. Alternative visits may take place instead of on-site visits until such time that the patient can safely return to the site. The process for obtaining remote informed consent must be followed if alternative study visits will be conducted ([Section 18.3](#)).

Throughout the study, the scheduling of study visits should adhere to the overall study schedule and visit windows defined in the protocol. For each study visit, all study procedures and assessments should be performed or completed in accordance with the schedule of events. Local institutions or other alternatives may be utilized.

Importantly, in instances in which the final scheduled study visit is not possible to be conducted at the study site, the final scheduled study visit should be performed all or by an alternative visit within the protocol-defined visit window. Critical data that pertain to the primary and secondary endpoints and other information such as adverse events, concomitant medications, use of feeding or ventilatory support, or other safety data that may be obtained remotely should be collected as part of the final study visit and within the protocol-defined visit window.

Procedures such as laboratory and other safety assessments that cannot be performed or obtained as part of a remote visit may be performed separately and preferably within the protocol-defined visit window.

Additionally, a Data Safety Monitoring Board/Data Monitoring Committee (DSMB/DMC) will review safety data on a quarterly basis. A detailed description of the DSMB/DMC, its role in this trial, and the timing and process of the scheduled reviews will be described in a DSMB/DMC Charter.

7.2. Number of Patients

At least 6 patients was planned to be enrolled as part of the combined analysis with Study AVXS-101-CL-302. At the time of this protocol was amended (Protocol version 6.0 amendment 5 dated 11 Nov 2020), the enrollment was closed with 2 active enrolled patients as the combined analysis is no longer to be performed.

7.3. Criteria for Trial Termination

An independent DSMB/DMC will conduct quarterly and ad hoc reviews of the emerging safety data throughout the trial as described in [Section 15](#).

The trial may be terminated for the following reasons:

- Development of unacceptable toxicity, defined as the occurrence of any unanticipated CTCAE Grade 3 or higher AE/toxicity that is possibly, probably, or definitely related to gene replacement therapy, and is associated with clinical symptoms and/or requires medical treatment.
- DSMB/DMC can recommend early termination of the trial for safety reasons.
- Trial is terminated by Sponsor.
- Regulatory Authority recommendation.

8. ELECTION AND WITHDRAWAL OF PATIENTS

Patients with SMA Type 1 who are < 6 months (< 180 days) of age at the time of gene replacement therapy (Day 1) with proven biallelic mutations of the *SMN1* gene and one or 2 copies of the *SMN2* will be enrolled in this trial.

8.1. Patient Inclusion Criteria

Patients must meet all of the following inclusion criteria:

1. Patients with SMA Type 1 as determined by diagnosis of SMA based on gene mutation analysis with biallelic *SMN1* mutations (deletion or point mutations) and one or 2 copies of *SMN2* [inclusive of the known *SMN2* gene modifier mutation (c.859G>C)]
2. Patients must be < 6 months (< 180 days) of age at the time of AVXS-101 infusion
 - a. Patients must have a swallowing evaluation test performed prior to administration of gene replacement therapy
 - b. Up-to-date on childhood vaccinations as per local health authorities.
 - c. Parent(s)/legal guardian(s) willing and able to complete the informed consent process and comply with trial procedures and visit schedule

8.2. Patient Exclusion Criteria

Patients must not meet any of the following exclusion criteria:

1. Previous, planned or expected scoliosis repair surgery/procedure prior to 18 months of age
2. Use of invasive ventilatory support (tracheotomy with positive pressure) or pulse oximetry < 95% saturation at screening
 - a. Pulse oximetry saturation must not decrease \geq 4 percentage points between screening and dosing with confirmatory oximetry reading
 - b. Patients may be put on non-invasive ventilatory support for less than 12 hours per day at the discretion of their physician or trial staff
3. Use or requirement of non-invasive ventilatory support for 12 or more hours daily in the two weeks prior to dosing
4. Patient with signs of aspiration based on a swallowing test or whose weight-for-age falls below the 3rd percentile based on World Health Organization (WHO) Child Growth Standards [[WHO 2006](#)] and unwilling to use an alternative method to oral feeding
5. Active viral infection (includes human immunodeficiency virus [HIV] or positive serology for hepatitis B, C, or E, or known Zika virus infection)
6. Serious non-respiratory tract illness requiring systemic treatment and/or hospitalization within 2 weeks prior to screening
7. Upper or lower respiratory infection requiring medical attention, medical intervention, or increase in supportive care of any manner within 4 weeks prior to screening

8. Severe non-pulmonary/respiratory tract infection (e.g., pyelonephritis, or meningitis) within 4 weeks before administration of gene replacement therapy or concomitant illness that, in the opinion of the Principal Investigator, creates unnecessary risks for gene replacement such as:
 - a. Major renal or hepatic impairment
 - b. Known seizure disorder
 - c. Diabetes mellitus
 - d. Idiopathic hypocalciuria
 - e. Symptomatic cardiomyopathy
9. Known allergy or hypersensitivity to prednisolone or other glucocorticosteroids or their excipients
10. Concomitant use of any of the following: drugs for treatment of myopathy or neuropathy, agents used to treat diabetes mellitus, or ongoing immunosuppressive therapy, plasmapheresis, immunomodulators such as adalimumab, or immunosuppressive therapy within 3 months prior to gene replacement therapy (e.g., corticosteroids, cyclosporine, tacrolimus, methotrexate, cyclophosphamide, IV immunoglobulin, rituximab)
11. Anti-AAV9 antibody titer > 1:50 as determined by Enzyme-linked Immunosorbent Assay (ELISA) binding immunoassay. Should a potential patient demonstrate Anti-AAV9 antibody titer > 1:50, he or she may receive retesting within 30 days of the screening period and will be eligible to participate if the Anti-AAV9 antibody titer upon retesting is ≤ 1:50
12. Clinically significant abnormal laboratory values GGT, ALT, AST, total bilirubin >2x the ULN, creatinine ≥ 1.0 mg/dL, hemoglobin [Hgb] < 8 or > 18 g/dL; white blood cell [WBC] > 20,000 per cmm) prior to gene replacement therapy. Patients with an elevated bilirubin level that is unequivocally the result of neonatal jaundice shall not be excluded.
13. Participation in recent SMA treatment clinical trial (with the exception of observational cohort studies or non-interventional studies) or receipt of an investigational or commercial compound, product or therapy administered with the intent to treat SMA (e.g., nusinersen, valproic acid) at any time prior to screening for this trial. Oral beta-agonists must be discontinued at least 30 days prior to dosing. Inhaled albuterol specifically prescribed for the purposes of respiratory (bronchodilator) management is acceptable and not a contraindication at any time prior to screening for this trial
14. Expectation of major surgical procedures during the trial assessment period (e.g., spinal surgery or tracheostomy)
15. Parent(s)/legal guardian(s) unable or unwilling to comply with trial procedures or inability to travel for repeat visits
16. Parent(s)/legal guardian(s) unwilling to keep trial results/observations confidential or to refrain from posting confidential trial results/observations on social media sites
17. Parent(s)/legal guardian(s) refuses to sign consent form
18. Patients < 35 weeks gestational age at time of birth

8.3. Patient Withdrawal Criteria

Patients may be discontinued from the trial for the following reasons:

- Death
 - An autopsy and/or post-mortem tissue/organ collection will be requested for any patient who expires following participation (see Post-Mortem Tissue and Organ Collection Plan in [Appendix 2](#)) as allowed per country/regional laws/regulations
- Failure to comply with protocol-required visits or trial procedures for 3 or more consecutive visits that are not rescheduled, unless due to hospitalization
- Parent(s)/legal guardian(s) withdraws consent
- Investigator discretion

End-of-trial procedures should be completed within 14 days for any patient who prematurely discontinues the trial for any reason, as indicated in [Appendix 1](#). Patients who terminate the study early for reasons other than death will be offered enrollment in a long-term follow-up study.

In instances in which a patient withdraws from the study prior to the last scheduled visit, the investigator should differentiate between factors that are related to a catastrophe (such as the inability to travel, local ordinances or other restrictions, etc.) versus withdrawal of consent.

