9.3. Treatment Compliance

AVXS-101 will be administered as a one-time IV injection.

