11. ASSESSMENT OF EFFICACY

Efficacy will be assessed by achievement of the key developmental milestone of sitting without support for at least 10 seconds at any time up to and including the 18 months of age trial visit and survival at 14 months of age (as defined in [Section 14.1.1](#)). Efficacy assessments will be performed at the times specified in the Schedule of Assessments ([Appendix 1](#)) and should be the first assessments performed at any scheduled visit. All post-treatment visits will be relative to the date on which gene replacement therapy is administered until the patient is 14 months of age, after which all visits will be relative to the patient's date of birth.

In the event of unforeseen catastrophe or other serious situation (such as the COVID-19 pandemic) that occurs during the study, which limits or prevents on-site study visits, alternative methods of data collection pertaining to efficacy assessments may be considered. Critical data that pertain to the primary and secondary endpoints should be collected according to the overall study schedule and within the protocol-defined visit window. The maintenance of the overall visit schedule and visit windows is especially important for the final scheduled study visit, as this may impact the overall interpretation of the evaluation of efficacy. As described in [Section 7.1](#), allowances are made for the collection of data remotely, when necessary.

Video recordings demonstrating the attainment of any new developmental milestones should be obtained within the protocol-defined visit window, including those that are required to be assessed as part of the final study visit or are related to primary or secondary endpoints (e.g., sitting without support). This may include submission of recordings made by the family or others as described in [Section 11.3](#).

Alternative methods of data collection for efficacy assessments depending on local regulations, institutional policies, and capabilities may include:

- developmental/motor efficacy assessments by a qualified clinical evaluator during a visit to the participant's home
- home videos or other recordings which demonstrate the achievement of developmental milestones that are specified in the protocol, including those to be assessed at the final scheduled study visit

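### Section 8.3 lets a consenting infant be discontinued from the trial for three missed visits after the only dose, and neither document requires the 14- and 18-month outcomes to be sought afterwards

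*Protocol*

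**What the plan says.** Protocol Section 8.3 opens its list with "Patients may be discontinued from the trial for the following reasons". One entry is "Failure to comply with protocol-required visits or trial procedures for 3 or more consecutive visits that are not rescheduled, unless due to hospitalization". Withdrawal of consent and investigator discretion are separate entries, so the missed-visit ground applies to families who still consent.

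Section 9.3 describes treatment in one line: "AVXS-101 will be administered as a one-time IV injection".

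Section 8.3 also softens the consequence of stopping. It says "End-of-trial procedures should be completed within 14 days for any patient who prematurely discontinues the trial for any reason" and "Patients who terminate the study early for reasons other than death will be offered enrollment in a long-term follow-up study". Section 7.1 places that study under a separate protocol.

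Remote contact is described in Sections 7.1 and 11. Section 7.1 says "Alternative visits include phone calls, virtual contacts through teleconsult or videoconference" as well as home visits, but under a condition: "In the event that unforeseen catastrophic or other serious situations (such as the COVID-19 pandemic) impact the ability to conduct the study on-site". Section 11, under the same kind of condition, says "allowances are made for the collection of data remotely, when necessary" and refers back to Section 7.1. Section 11.3 accepts milestone videos from parents at any time during the trial.

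The primary endpoint is sitting at any visit up to 18 months of age (Section 14.1.1). The secondary endpoint is survival free of permanent ventilation at 14 months (Section 14.1.2). Both are listed only (Sections 14.1 and 14.4.2). Enrollment was closed with 2 patients (Section 7.2).

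**The concern.** In a trial with repeated dosing, missed visits can be a reason to stop the drug. Here no study product is left to stop once the infusion is done, so discontinuation for missed visits only ends data collection.

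The two efficacy endpoints are fixed by age, and the rule can be met months before either age. If it is applied, a first sit that comes later, or the child's ventilation-free status at 14 months, may never reach the listings, although the parents have not withdrawn consent. The listings are the only efficacy output, and there are two patients, so a single gap is conspicuous. Safety data are also cut short: Section 13.1.1 collects adverse events only through the last trial visit.

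**Working it through.** The plan states no power, alpha or dropout figure to reproduce, so the check is date arithmetic and a reading of what is collected after discontinuation.

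**Inputs**
- Oldest age at dosing: 179 days (under 180 days; Protocol Section 8.1).
- First three outpatient visits: Days 7, 14 and 21. Months 3, 4 and 5 fall at Days 90, 120 and 150 (Protocol Appendix 1, 30-day months).
- Age in days = date − date of birth + 1, and dosing is on Day 1 (SAP Sections 2.1.1 and 2.3.2). So age on study day d = age at dosing + d − 1.
- 14 months = 14 × 30 = 420 days; 18 months = 18 × 30 = 540 days.
- End-of-trial procedures up to 14 days after discontinuation (Protocol Section 8.3).

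**How early the rule can be met**

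| Age at dosing | Visits missed | Age at third missed visit | Days left to 14 months | Days left to 18 months |
|---|---|---|---|---|
| 179 | Days 7, 14, 21 | 179 + 20 = 199 | 420 − 199 = 221 | 540 − 199 = 341 |
| 179 | Months 3, 4, 5 | 179 + 149 = 328 | 420 − 328 = 92 | 540 − 328 = 212 |
| 1 | Days 7, 14, 21 | 1 + 20 = 21 | 420 − 21 = 399 | 540 − 21 = 519 |

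If the end-of-trial visit takes place 14 days after the third missed visit, subtract 14. The first row becomes 207 and 327 days, the second 78 and 198, the third 385 and 505. These are nominal days; visit windows move them slightly.

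**What is kept**
- A sit already confirmed on video. It counts at any visit, and its date is that of the earliest confirming video (Protocol Sections 14.1.1 and 11.3).
- A death or permanent ventilation that has already occurred.
- The 14-month endpoint, if discontinuation comes after 14 months.

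**What is at risk**
- A first sit after discontinuation.
- Event-free status at 14 months, if the infant is event-free when discontinued before that age.

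**Routes to those outcomes after discontinuation**
- The end-of-trial procedures give status on that date, not at 14 or 18 months.
- Long-term follow-up is an offer under another protocol. Neither document says its data may complete this trial's endpoints.
- Remote visits are written for catastrophic or other serious situations, so they do not clearly cover an ordinary missed visit.
- Family videos are accepted during the trial; no extension past discontinuation is stated.
- SAP Section 2.1.1 defines last contact as the last study visit. SAP Sections 2.5.4 and 2.6.4 mark missing-value handling as not applicable, and SAP Section 5.1 does not impute endpoints.
- Protocol Section 14.4.2 calls for a dichotomous result for each patient. Neither document says whether an infant discontinued before sitting is shown as not achieved or as missing.

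**Share affected:** one infant is 1 of the 2 enrolled.

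**The case against.** The case for leaving the text alone is substantial. The rule is permissive, and it spares rescheduled visits and absences due to hospitalization. The end-of-trial column of Appendix 1 also serves early termination and includes milestones with video, so a discontinued infant should have a closing assessment. Endpoints are not formally analyzed, and leaving values unimputed in individual listings is appropriate. SAP Section 2.3.1 reports who is still in the study at 14 and 18 months and why others left, so a gap would be visible. A family that misses three visits may not answer calls or send videos either. With two patients and completion of the last patient estimated for Q3 2021, the rule may never have been used.

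Most of this stands, and it limits the size of the point. It does not close the gap. Optional use leaves retention of endpoint data to discretion, and the closing assessment may come months before the endpoint ages.

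Three stronger readings are tempting:
- A reader might infer that one discontinuation removes half of the efficacy and long-term safety data. It does not: data already collected remain, and long-term follow-up is still offered.
- A reader might infer that outcome-related missing data would bias a result. No estimate or test is planned, and the documents give no evidence that missed visits track the child's condition. It is plausible for a frail child cared for at home, but that is an assumption.
- A reader might infer that the protocol already provides phone and video contact for ordinary missed visits. The condition in Section 7.1 does not support that. Nor could a phone call supply the primary endpoint, which SAP Section 2.5.1 bases only on milestones confirmed by the independent reviewer.

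**Conclusion.** The point holds in a limited form. Section 8.3 allows follow-up of a consenting family to be ended for missed visits when there is no study product left to stop, and nothing requires the endpoint outcomes to be sought afterwards. The earliest outpatient trigger leaves 221 days to the secondary endpoint age and 341 days to the primary endpoint age for the oldest eligible infant, and more for younger ones.

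The consequence is an incomplete listing for at most the later outcomes of a discontinued infant. No power, error rate or estimate changes. This assumes that discontinuation is actually applied, that the infant had not already sat or had an event, and that long-term follow-up data are not used to fill the gap. The documents do not say whether either infant met the rule. They also do not say whether both belong to the ITT population, for which the endpoints are listed; if only one does, that infant would be the whole efficacy listing. This is a low-cost improvement, not a flaw that undermines the trial.

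**What to change.** 1. In Protocol Section 8.3, state that missed visits alone, including under investigator discretion, do not end follow-up unless consent is withdrawn. Deleting the missed-visit entry without this would leave the discretion entry as the same route.
2. In Protocol Sections 7.1 and 11, extend the remote options explicitly to ordinary missed visits. Use them to obtain survival and ventilation status at 14 months, and a sitting video up to 18 months that goes to central review.
3. State in the protocol and SAP whether long-term follow-up data may complete the listings, and how an infant discontinued before sitting is shown.

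The cost is wording and a few remote contacts. Some families may still not respond, so the change reduces the gap without guaranteeing complete data. The third item needs no new contact with families and could still be settled before database lock.
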